#### General

- 21. Subject consumes more than 25 g of alcohol per day. (Refer to Appendix 12.5)
- 22. Subject who currently follows an excessive weight reduction diet in the opinion of the investigator.
- 23. Subject currently engages in a vigorous exercise regimen (e.g.; marathon training, body building training etc.) or intends to start training during the study.
- 24. Subject has hypersensitivity or intolerance to Ezetimibe or Rosuvastatin.
- 25. Subject has a history of myopathy or rhabdomyolysis with Ezetimibe or any statin.
- 26. Subject is currently pregnant or lactating.

MK-0653H-832-01 Final Protocol

**Protocol/Amendment No.:** 832-01

27. Subject is taking any other investigational drugs and/or has taken any investigational drugs within 30 days prior to the day of signing informed consent, unless pharmacokinetics necessitates a longer washout.

# <Visit 2: Placebo run-in, Week -2>

28. Subject has taken lipid-lowering agents (except probucol) including fish oils, CholestinTM, bile acid sequestrants, statins, Ezetimibe, fibrates or niacin (>200 mg/day) within 6 weeks prior to Visit 2. Subject has taken probucol or protein convertase subtilisin/kexin type 9 (PCSK 9) inhibitor within 10 weeks prior to Visit 2.

### <Visit 1 to 3>

- 29. Subject has developed a new medical condition, suffered a change in status of an established medical condition or required a new tratement or medication, which meets any previously described study exclusion criteria.
- 30. The subject who is considered inappropriate for participation in the study by the investigator for any other reason.
- 31. Subject Is or has an immediate family member (e.g., spouse, parent/legal guardian, sibling or child) who is investigational site or sponsor staff directly involved with this trial.

# 5.2 Trial Treatment(s)

The treatment(s)to be used in this trial is outlined below in Table 1.

Table 1 Trial Treatment

Treatment group	Study Drug Containers Dispensed		
Treatment group	Bottle A	Blister card B	Blister card C
Placebo run-in period (single-blind)	Ezetimibe Placebo tablet	Rosuvastatin Placebo capsule	Rosuvastatin Placebo capsule
Treatment period (double-b	lind)		
Ezetimibe	Ezetimibe	Rosuvastatin	Rosuvastatin
10 mg	10 mg tablet	Placebo capsule	Placebo capsule
Rosuvastatin	Ezetimibe	Rosuvastatin	Rosuvastatin
2.5 mg	Placebo tablet	2.5 mg capsule	Placebo capsule
Rosuvastatin	Ezetimibe	Rosuvastatin	Rosuvastatin
5 mg	Placebo tablet	2.5 mg capsule	2.5 mg capsule
MK-0653H	Ezetimibe	Rosuvastatin	Rosuvastatin
(EZ 10 mg+Ros 2.5 mg)	10 mg tablet	2.5 mg capsule	Placebo capsule
MK-0653H	Ezetimibe	Rosuvastatin	Rosuvastatin
(EZ 10 mg+Ros 5 mg)	10 mg tablet	2.5 mg capsule	2.5 mg capsule

**Protocol/Amendment No.:** 832-01

The first dose of trial treatment will be administered at the trial site at Visit 2. Subsequent dosing will be performed once daily by the subject (i.e., unsupervised at his/her home) at approximately the same time each day.

The investigator shall take responsibility for and shall take all steps to maintain appropriate records and ensure appropriate supply, storage, handling, distribution and usage of trial treatments in accordance with the protocol and any applicable laws and regulations.

## **5.2.1** Dose Selection

# **5.2.1.1** Dose Selection (Preparation)

The rationale for selection of doses to be used in this trial is provided in Section 4.0 – Background & Rationale. There are no specific calculations or evaluations required to be performed in order to administer the proper dose to each subject.

# **5.2.2** Timing of Dose Administration

Study drug will be administered orally once daily after meal. As there is no recommended time for the dosage, subject should take their treatment at a consistent time each day to promote compliance. On the visit day, subject should take the medication after all procedure is completed. The scheduled last study drug is a day before Visit6.

# 5.2.3 Trial Blinding

A single-blinding technique will be used. In Placebo Run-in period, Ezetimibe 10 mg matching placebo tablet and Rosuvastatin 2.5 mg matching placebo capsule will be packaged identically so that blind/masking is maintained. The subject will not know the treatment they are administered, however the investigator and Sponsor personnel or delegate(s) who are involved in the treatment or clinical evaluation of the subjects will be aware of the group assignments.

A double-blinding technique will be used. In treatment period, Ezetimibe 10 mg tablet and Rosuvastatin 2.5 mg capsule will be packaged identically relative to their matching placebos so that blind/masking is maintained. The subject, the investigator and Sponsor personnel or delegate(s) who are involved in the treatment or clinical evaluation of the subjects are unaware of the group assignments.

See Section 7.1.4.2, Blinding/Unblinding, for a description of the method of unblinding a subject during the trial, should such action be warranted.

#### **Randomization or Treatment Allocation**

Treatment allocation/randomization will occur centrally using an interactive voice response system / integrated web response system (IVRS/IWRS). There are 5 treatment arms. Subjects will be assigned randomly in a 1:2:2:2:2 ratio to Ezetimibe 10 mg, Rosuvastatin 2.5 mg, Rosuvastatin 5 mg, MK-0653H (EZ 10 mg+Ros 2.5 mg) and MK-0653H (EZ 10 mg+Ros 5 mg), respectively.

## Stratification

Treatment allocation/randomization will be stratified according to the following factors:

MK-0653H-832-01 Final Protocol Confidential 04R355IV4

**Protocol/Amendment No.:** 832-01

To achieve balance across treatment groups, randomization will be stratified according to the risk category determined at Visit 3.

- 1. Category I
- 2. Category II
- 3. Category III

#### 5.5 Concomitant Medications/Vaccinations

Medications or vaccinations specifically prohibited in the exclusion criteria are not allowed during the ongoing trial. If there is a clinical indication for any medication or vaccination specifically prohibited during the trial, discontinuation from trial therapy or vaccination may be required. The investigator should discuss any questions regarding this with the Sponsor Clinical Director. The final decision on any supportive therapy or vaccination rests with the investigator and/or the subject's primary physician. However, the decision to continue the subject on trial therapy or vaccination schedule requires the mutual agreement of the investigator, the Sponsor and the subject.

Concurrent antihypertensive, and antihyperglycemic medications are permitted. It is preferable that doses of these medications remain stable throughout the study.

# 5.6 Rescue Medications & Supportive Care

No rescue or supportive medications are specified to be used in this trial.

# 5.7 Diet/Activity/Other Considerations

## 5.7.1 Diet

Subjects should be instructed on JAS2012 diet or a similar diet at Visit 1. Please refer to Appendix 12.5 for details on the diet regimen.

At each subsequent study visit, the dietary compliance will be monitored and sites should reinstruct subjects who are not compliant. This monitoring is particularly important in an effort to minimize any diet-related lipid changes.

### 5.7.2 Activity

Subjects should continue any activity he/she was accustomed to prior to entering the study (including smoking), but should refrain from engaging in a vigorous exercise regimen and initiating smoking during the study. Subjects should be instructed the activity by investigator based on JAS2012 guideline. Subject also should keep exclusion criterion #22 and #23. (Subject does not follow excessive weight reduction diet from study duration, and does not engage in a vigorous exercise regimen or start training) during the study.

## 5.7.3 Alcohol Intake

Subjects should not consume more than the 25 g alcohol per day, and should not have any alcohol within 24 hours prior to scheduled visit.

04ROSM Confidential

Protocol/Amendment No.: 832-01

Subjects will not be permitted in the study if they consistently consume excessive amounts of alcohol. Subjects should be encouraged not to make major changes in their alcohol consumption for the duration of the study. Please refer to Appendix 12.5 for reference volume of alcohol

# 5.7.4 Contraception

Women of reproductive potential can be entered in the study (see inclusion criteria #4) and must agree to use 2 acceptable methods of contraception during sexual activity with a male partner. These contraceptive methods must be used throughout the study. Acceptable methods of contraception are either 2 barrier methods to prevent pregnancy. The following are considered acceptable barrier methods of contraception: intrauterine device (IUD), diaphragm with spermicides, condoms, partner or vasectomy. Contraception medications are restricted in exclusion criteria #16 and #17.

# 5.8 Subject Withdrawal/Discontinuation Criteria

Subjects may withdraw consent at any time for any reason or be dropped from the trial at the discretion of the investigator should any untoward effect occur. In addition, a subject may be withdrawn by the investigator or the Sponsor if enrollment into the trial is inappropriate, the trial plan is violated, or for administrative and/or other safety reasons. Specific details regarding discontinuation or withdrawal procedures are provided in Section 7.1.4 – Other Procedures.

Table 2 provides reasons why a subject must be discontinued from treatment but may continue to be monitored in the trial, as well as reasons why a subject must be discontinued from treatment and the trial.

Table 2 Discontinuation Scenarios

Reason for Discontinuation Scenario	Action				
The subject or legal representative (such as a parent	Discontinuation from Treatment and Trial				
or legal guardian) withdraws consent.					
The subject's treatment assignment has been	Discontinuation from Treatment and Trial				
unblinded by the investigator, Merck subsidiary or					
through the emergency unblinding call center					
Consecutive (2 or more measurements) elevations in	Discontinuation from Treatment and Trial				
ALT and/or AST $\geq 3 \times ULN$					
Consecutive elevations in CK $\geq$ 10 x ULN with or	Discontinuation from Treatment and Trial				
without muscle symptoms.					
Consecutive elevations in CK $\geq$ 5 to <10 x ULN	Discontinuation from Treatment and Trial				
with muscle symptoms.					
Subject requiring any treatment with cyclosporine	Discontinuation from Treatment and Trial				
or fibrates.					
Pregnancy (Positive serum pregnancy test): A	Discontinuation from Treatment and Trial				
positive urine pregnancy test requires immediate					
interruption of study drug while awaiting results of					
serum pregnancy (β-hCG) test.					
Any subject who is unblinded to treatment regimen	Discontinuation from Treatment and Trial				
during study. (The subject's treatment assignment					
has been unblinded by subject him/herself.)					
Adverse experiences: Subject may be withdrawn	Discontinuation from Treatment and Trial				
from the study in the event that the investigator					

04REM Confidential

Protocol/Amendment No.: 832-01

Reason for Discontinuation Scenario	Action
assesses that administration of the study drug should	
be discontinued due to the occurrence of adverse	
experiences which would interfere with study	
continuation.	
Serious deviation from the protocol: It becomes	Discontinuation from Treatment and Trial
inappropriate to continue study treatment as a result	
of a significant protocol deviation.	
Lost to follow up: When a subject stops visiting a	Discontinuation from Treatment and Trial
site after initiation study drug, he/she will be	
contacted via a letter or telephone call to confirm	
the reason for missed visits, dosing of study drug	
and the subsequent courses as much as possible.	
Moved (or relocated): When subject has either	Discontinuation from Treatment and Trial
moved or relocated and is no longer able to	
participate in the study.	
The subject has a medical condition or personal	Discontinuation from Treatment and Trial
circumstance which, in the opinion of the	
investigator and/or Sponsor, places the subject at	
unnecessary risk through continued participation in	
the trial or does not allow the subject to adhere to	
the requirements of the protocol.	

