3. Myopathy or Rhabdomyolysis are to be reported as ECI because of their association with lipid-lowering treatments. If a subject is reported as having myopathy, rhabdomyolysis, or if the CPK criterion necessitating study medication discontinuation is met, this constitutes an ECI. ECIs will be recorded in the database, monitored by the SPONSOR and reported in the clinical study report.

**Protocol/Amendment No.:** 832-01

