p-Values (Tier 1 only) for treatment comparisons and 95% CIs for between-treatment differences in the percentage of subjects with respective Tier 1 and Tier 2 events will be

MK-0653H-832-01 Final Protocol Confidential 04RWM

**Protocol/Amendment No.:** 832-01

calculated using the Miettinen and Nurminen method. The analysis will not be stratified by risk category.

**Protocol/Amendment No.:** 832-01

Table 5 Analysis Strategy for Safety Parameters

Safety		p-	95% CI for	Descriptive
tier	Safety endpoint †	Value	treatment difference	statistics
Tier 1	
 
gastrointestinal related AEs
 
gallbladder-related AEs
 
allergic reaction or rash AEs
 
hepatitis-related AEs
 
consecutive elevations in ALT ≥3x ULN
 
consecutive elevations in AST ≥3x ULN
 
consecutive elevations in ALT or AST ≥3x ULN
 
ALT or AST ≥5x ULN
 
AST elevations ≥5x ULN
 
ALT or AST elevations ≥5x ULN
 
ALT elevations ≥10 x ULN
 
AST elevations ≥10x ULN
 
ALT or AST elevations ≥10x ULN
 
potential Hy's Law condition (ALT or AST elevations >3x ULN, with ALP <2x ULN and TBL ≥2x ULN)
 
CK elevations ≥10x ULN
 
CK elevations ≥10x ULN with muscle symptoms
 
CK elevations ≥10x ULN with muscle symptoms that are considered drug-related
 
	X	X	X
Tier 2	
 
AE
 
drug-related AE
 
SAE
 
drug-related SAE
 
discontinuation due to AE
 
discontinuation due to drug-related AE
 
discontinuation due to SAE
 
discontinuation due to drug-related SAE
 
specific AEs, SOCs (incidence ≥4 subjects in at least one treatment group)
 
Specific AEs, or SOCs‡ (incidence <4
 
		X	X
	
 
subjects in all treatment groups)
 
Change from baseline results (laboratory, and vital signs)
 
			X
' AE re	ferences refer to both clinical and laboratory AEs.			

AE references refer to both clinical and laboratory AEs.

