## 12.6 Standard Operating Procedure for Liver and Muscle Enzyme Evaluations

Every increase in ALT, AST, and/or CK above the limits described in the protocol (i.e., ALT/AST  $\geq$ 3 times the upper limit of normality [ULN], and CK  $\geq$ 5 times ULN), the central laboratory will alert the investigators/ coordinators and the SPONSOR clinical personnel. The study and central laboratory SOP calls for immediate repeat testing within 3 days every time these tests reach these limits or are otherwise questionable.

Under these circumstances, the investigators/coordinators must recall the subject and attempt to identify the cause of the elevation. This evaluation should include:

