#### 2. Actions

- Patients with persistent (2 or more) CK elevations between 5 and <10 times the ULN and muscle symptoms will also be discontinued.
- Patients with persistent (2 or more) CK elevations between 5 and <10 times the ULN without symptoms may remain on drug (at the discretion of the SPONSOR medical monitor) with more intensive monitoring (as agreed to by the monitor and investigator). These patients should remain on drug until repeat labs are obtained.
- Patients with persistent (i.e., 2 consecutive measurements), unexplained 10 fold elevation in CK with or without symptoms will be discontinued from the study.

NOTE: All discontinued patients should be monitored and have repeat lab draws completed until critical elevations have resolved.

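### With muscle symptoms, two consecutive CK values of 5 to <10 × ULN force discontinuation, but a pair straddling 10 × ULN (8× then 14×, or 12× then 9×) meets neither mandatory CK rule

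*Combined protocol and SAP*

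**What the plan says.** Section 5.8, Table 2 lists the situations in which a subject has to be taken off treatment. Two rows concern CK, and both lead to discontinuation from treatment and trial:

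- Upper band: "Consecutive elevations in CK $\geq$ 10 x ULN with or" without muscle symptoms.
- Lower band: "Consecutive elevations in CK $\geq$ 5 to <10 x ULN", applying only with muscle symptoms.

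Appendix 12.6, part A.2 has matching actions. For the lower band: "Patients with persistent (2 or more) CK elevations between 5 and <10 times the ULN and muscle symptoms will also be discontinued". For the upper band: "Patients with persistent (i.e., 2 consecutive measurements), unexplained 10 fold elevation in CK with or without symptoms will be discontinued from the study". Subjects in the lower band without symptoms may stay on drug at the sponsor medical monitor's discretion, with closer monitoring.

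Three other provisions bear on the point.

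- Section 7.2.3.2 ties event-of-clinical-interest (ECI) reporting to the same rule: "if the CPK criterion necessitating study medication discontinuation is met, this constitutes an ECI". Myopathy and rhabdomyolysis are ECIs in their own right.
- For CK of at least 5 × ULN, Appendix 12.6 "calls for immediate repeat testing within 3 days every time these tests reach these limits", and the central laboratory alerts the site and the sponsor's clinical personnel.
- Table 2 also has an adverse-experience row and a row for subjects placed at "unnecessary risk through continued participation in" the trial. Both rest on the judgement of the investigator, or of the investigator and sponsor.

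**The concern.** A stopping rule should be monotone: if one pattern forces a stop, a worse pattern should too. For symptomatic subjects this one is not. The lower band has a ceiling of <10 × ULN, and both consecutive values must fall inside it. A second value of 14× after 8× takes the pair out of the lower band without putting it in the upper one.

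The ceiling is also out of line with neighbouring rules. The ALT/AST row in Table 2 is an open floor (consecutive values of at least 3 × ULN), so 4× then 12× stops. The CK alert limit in Appendix 12.6 is likewise an open floor, at 5 × ULN.

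At stake is an automatic muscle-safety stop in a trial where every subject receives a statin, ezetimibe or both. The CPK limb of the ECI definition follows the same rows. A straddling pair therefore does not trigger 24-hour reporting by that route.

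**Working it through.** The plan states no figure to reproduce; the check is of the logic of the rules.

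**Inputs.** For a symptomatic subject, let L be a CK value of 5 to <10 × ULN and H a value of at least 10 × ULN. Table 2 stops a subject on two consecutive H or two consecutive L. The ALT/AST row of Table 2 gives consecutive as two or more measurements.

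**Specific pairs, with symptoms, under the literal Table 2 rules:**

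| CK (× ULN) | CK row met? | With the cap removed |
|---|---|---|
| 5, 5 | yes (lower) | yes |
| 8, 9 | yes (lower) | yes |
| 14, 14 | yes (upper) | yes |
| 8, 14 | no | yes |
| 12, 9 | no | yes |
| 9.9, 10 | no | yes |
| 9.9, 40 | no | yes |

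**All two-value patterns.** LL and HH stop; LH and HL do not: 2 of 4 assigned.

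**All three-value patterns, every value at least 5 × ULN:**

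- LLL, LLH, HHH and HHL stop at the second value: 4.
- LHH and HLL stop only at the third value: 2. Examples are 8/14/12 and 12/9/8.
- LHL and HLH meet no row: 2. Examples are 8/14/9 and 12/9/11.

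So 4 + 2 = 6 of 8 are assigned. Of the four sequences that begin with a straddling pair, two stop one retest late and two stay open.

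**Generous reading of Appendix 12.6.** The lower-band bullet asks for two or more elevations without saying they must be consecutive; the upper-band bullet does say so. If any two L values suffice, LHL also stops and 7 of 8 are assigned. HLH has one L and no consecutive H, so it stays open. The two-value count is still 2 of 4.

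**Third value below 5 × ULN.** After a straddling pair, neither row is met, and the elevation is resolving.

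**Cap removed** (two consecutive values of at least 5 × ULN with symptoms): 4 of 4 pairs and 8 of 8 triples are assigned.

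**Without symptoms.** Both-low may stay on drug, a straddling pair meets no mandatory row, and both-high must stop. That ordering is consistent, so the problem is confined to symptomatic subjects.

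**The case against.** The best reply is that this is a drafting slip with little practical effect. The bands are probably meant as floors, with symptoms lowering the threshold from 10× to 5×, and most investigators would probably read them that way. The retest within 3 days soon gives a third value, and sponsor clinical staff are alerted each time. Section 5.8 lets the investigator withdraw a subject for any untoward effect, and lets the investigator or the sponsor do so for safety reasons. Myopathy and rhabdomyolysis are ECIs regardless, and the Tier 1 analysis in Section 8.6.2 still counts "CK elevations ≥10x ULN with muscle symptoms".

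Numbers should also be small. Entry requires CK of no more than 3 × ULN, prior myopathy or rhabdomyolysis on ezetimibe or a statin is excluded, and treatment lasts 12 weeks. The 52-week post-marketing survey in Section 4.1.2 reports drug-related CPK increase in 2.26%. If that rate carried over, which is an assumption, it would give 0.0226 × 306 ≈ 7 subjects with any such event; symptomatic straddling pairs would be a small subset.

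Two narrower points are fair. A fall from 12× to 9× is a less clear case of worsening than a rise from 8× to 14×. And Appendix 12.6 limits its upper-band stop to unexplained elevations, a qualifier that an uncapped symptomatic bullet would bypass.

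The arguments on size and likely intent stand. They do not supply the missing automatic stop: the discretionary routes rest on opinion, and the retest still leaves one or two of the eight patterns open. If the intent is a floor, the text should say so. The overlap over unexplained elevations adds no new stop, because the Table 2 upper row already stops both-high pairs without that qualifier.

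**Conclusion.** The concern holds on the wording of Table 2, and Appendix 12.6 does not cure it. For symptomatic subjects, the mandatory rule stops 6× then 6× but not 8× then 14×. Two of four two-value patterns are unassigned. After the retest, with all values at least 5 × ULN, two of eight remain so, or one of eight on the generous reading.

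This rests on reading the bands literally and on muscle symptoms being present throughout. The likely consequence is a stop delayed by one retest or left to clinical judgement, and an ECI trigger that does not fire by the CPK route. No efficacy endpoint, estimate, error rate or power figure is affected. It should be corrected because a stated mandatory safety rule orders severity wrongly.

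**What to change.** In the lower-band CK row of Table 2 and the first bullet of Appendix 12.6, part A.2, replace the capped band with: *consecutive (2 or more) CK elevations ≥5 × ULN with muscle symptoms*. Leave the ≥10 × ULN rule and the asymptomatic bullet as they are. The CPK trigger in Section 7.2.3.2 then follows without further editing.

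The cost is one phrase in two places at the next amendment. No tests are added, since the repeat CK is already required. Nothing changes for asymptomatic subjects or, under Table 2, for pairs wholly within one band. The only downside is that a few more symptomatic subjects, those with straddling pairs, may be discontinued.

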# 5.9 Subject Replacement Strategy

A subject who discontinues from the trial will not be replaced.

